Objective: Utilizing a prospective randomized controlled trial, post-operative patient-reported VAS pain (on a scale of 0-10) will be collected 2 times per day (every 12 hours) for 7 post-operative days (PODs); then an average score collected on POD 14, POD 21, POD 28, and POD 42. Scores will be averaged and compared between the two treatment groups for the first 7 days, 2 week, 3rd week, 4th week and 6th week postoperatively.

Secondary Aims & Objectives

Aim 2a: To assess patient-reported outcomes and early range of motion (measured in morphine equivalents) in patients treated with flowable placental-derived pECM compared to patients injected with saline control.

Hypothesis: There will be improved patient reported outcomes and early range of motion measured at 6 weeks and 3 months and 6 months postoperatively in patients receiving and extracellular matrix injection following outpatient rotator cuff surgery.

Objective: Utilizing a prospective randomized controlled trial, patient reported outcomes as measured by American Shoulder and Elbow Score, Simple Shoulder Test and SANE scores and range of motion (External rotation, internal rotation and forward flexion) will be collected preoperatively and at 2 weeks (external rotation), 6 weeks (all) , 3 months (all) and 6 months (all) postoperatively. Scores and range of motion measurements will be averaged and compared for differences between the two groups.

Study Design

The study design is a randomized double-blind randomized controlled trial.

Research Design

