This is a double-blinded study, thus, neither the surgeon nor the patient will know if a pECM injection is used. A total of 70 envelopes will be generated consisting of 35 with Group 1” (no pECM) and 35 with “Group 2” (pECM Injection). Envelopes will be sealed and randomly chosen prior to surgery. Once the envelope is opened to determine if pECM is to be injected, the name of the patient will be added to the envelope along with the treatment group, and the envelope will be sealed. The treatment group and name of patient will be kept confidential until completion of the study. Envelopes will be opened at end of study for data collection and analysis purposes with patient information deidentified. They will be stored in a locked container at the surgery center only accessible by the chief of staff. Patients will be blinded to the treatment as well as the treating surgeon. The physician assistant will not be blinded as she will administer the injection for the treatment group but will keep the information confidential. She will not participate in follow-up data collection of the patients in this study postoperatively.

Study Visits/ Study Duration

Participants enrolled in this study will be followed for a period of 6 months post-operatively. For the first week, twice per day (12-hour increments), patients will self-report VAS pain and indicate their narcotic use (number of tablets ingested). Data concerning pain and narcotic use will be collected via text message (or phone if patients fail to respond to text messages).

Post-operative day (POD)	Data Collection Time	Data to be Collected
POD 0	8PM	VAS; #pain pills used
POD1	8AM	VAS; #pain pills used
	8PM	VAS; #pain pills used
POD2	8AM	VAS; # pain pills used
	8PM	VAS; # pain pills used
POD3	8AM	VAS; # pain pills used
	8PM	VAS; # pain pills used
POD4	8AM	VAS; # pain pills used
	8PM	VAS; # pain pills used
POD5	8AM	VAS; # pain pills used
	8PM	VAS; # pain pills used
POD6	8AM	VAS; # pain pills used
	8PM	VAS; # pain pills used

POD7	8AM	VAS; # pain pills used
	8PM	VAS; # pain pills used
POD14 (2 weeks)	Office Exam	ER (neutral); ASES; SANE; SST
	8PM	VAS; # pain pills used
POD21 (3 weeks)	8PM	VAS; # pain pills used
POD28 (4 weeks)	8PM	VAS; # pain pills used
POD42 (6 weeks)	Office Exam	ER (neutral and scapular/IR- scapular/FF; ASES; SANE; SST
	8PM	VAS; # pain pills used
3 months	Office Exam	VAS; ER (neutral and scapular/IR-scapular/FF; ASES; SANE; SST

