6 months	Office Exam	VAS; ER (neutral and scapular/IR-scapular/FF; ASES; SANE; SST

The enrollment period for study participation is anticipated to last for 12 months only for data analysis.

Specimen Collection, Preparation, Handling and Shipping

N/A

Statistical Analysis Plan

After data checking and validation are completed, the analysis of the data will begin with examination of the distribution of each of the study variables. In this process, outliers will be identified and evaluated for inclusion in the final study database. Appropriate summary statistics will be calculated. Means and standard deviations will be reported for normally distributed continuous variables, a median and range will be tabulated for continuous variable that are not normally distributed, and frequencies and percentages will be provided for categorical variables. The remainder of the analysis will correspond to the specific aims provided above.

Specific Aims 1a-b:

To determine if there is a difference in patient-reported post-operative narcotic use (measured in morphine equivalents) among two groups.

If data are normally distributed, analysis of variance (ANOVA) with Tukey's HSD pairwise comparisons will be used to compare narcotic use (converted to morphine equivalents) between the three groups at each PODs. Cumulative narcotic use during all PODs will also be compared between groups. If data are not normally distributed, then Kruskal-Wallis with Dunn's multiple comparisons tests will be used.

To determine if there is a difference in mean VAS pain between the control group and ECM group postoperatively.

If data are normally distributed, analysis of variance (ANOVA) with Tukey's HSD pairwise comparisons will be used to compare VAS pain between the two groups at each PODs 1-7, 14, 21, 28 and 42. If data are not normally distributed, then Kruskal-Wallis with Dunn's multiple comparisons tests will be used.

Specific Aim 2:

To determine if there is a difference in clinical and functional outcomes of patients with rotator cuff tears treated with the nanofiber scaffold compared to those treated without.

If data are normally distributed, independent t-tests will be used to compare VAS Pain, SANE, V-12, ASES, and ROM measures between the control and intervention groups at each preoperative and postoperative timepoint. If data are not normally distributed, then Mann-Whitney U tests will be performed.

Potential Risks and Benefits

Potential Risks

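### Aim 2 uses its required preoperative scores and motion only in unadjusted between-group tests, and its test list does not match the outcomes collected

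*Combined protocol and SAP*

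**What the plan says.** Secondary Aims & Objectives, Aim 2a, names ASES, SST and SANE as the patient-reported outcomes. It states that "Simple Shoulder Test and SANE scores and range of motion (External rotation, internal rotation and forward flexion) will be collected preoperatively" and again at postoperative visits, and that "Scores and range of motion measurements will be averaged and compared for differences between the two groups".

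Statistical Analysis Plan, Specific Aim 2, says that "independent t-tests will be used to compare VAS Pain, SANE, V-12, ASES, and ROM measures". The same sentence sets the scope of these tests as "between the control and intervention groups at each preoperative and postoperative timepoint". The alternative is also without a covariate: "If data are not normally distributed, then Mann-Whitney U tests will be performed". The same paragraph describes the comparison as "rotator cuff tears treated with the nanofiber scaffold compared to those treated without", whereas the intervention section gives pECM as the study product.

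The only other use of preoperative values is the general statement that "Appropriate summary statistics will be calculated". No ANCOVA, change score or other baseline adjustment appears anywhere.

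The table under Study Visits/ Study Duration starts on the evening of surgery and has no preoperative row. It schedules SST at 2 weeks ("ER (neutral); ASES; SANE; SST"), 6 weeks, 3 months and 6 months.

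**The concern.** Two separate things are at stake.

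The first is precision. A preoperative shoulder score or motion often carries information about the later value of the same measure. Where it does, adjusting for it narrows the interval for the group difference at no cost in patients. The plan instead uses the baseline in a significance test before treatment. Under randomisation the null hypothesis of that test is true by design, so any significant result is a chance finding that could be misread as a flaw in the trial.

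The second is that the analyst cannot carry out the list as written. SST is collected and is to be compared, but has no named test. V-12 has a named test, but nothing defines or schedules it. VAS is in a list tested at preoperative times, but its first scheduled collection is after surgery. If these points stay open, they will be settled with data in hand, which leaves room for selective reporting.

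**Working it through.** **1. Lists side by side**

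| Measure | Preoperative (Aim 2a) | Postoperative (visit table) | Test named (Specific Aim 2) |
|---|---|---|---|
| ASES | yes | yes | yes |
| SANE | yes | yes | yes |
| SST | yes | yes | **no** |
| Range of motion | yes: external rotation, internal rotation, forward flexion; no positions given | yes: external rotation in two positions from 6 weeks | yes |
| VAS | **no** | yes | yes |
| V-12 | **no** | **no** | yes |

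**2. Preoperative tests**

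Five measures have both a required baseline and a place in the test list: ASES, SANE and three motions. At 0.05 each, the chance of at least one significant result is 0.05 if they are fully correlated and 1 − 0.95^5 = 0.226 if they are independent.

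**3. Group size used**

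The Sample Size section gives 28 per group before attrition and 35 enrolled. The attrition step reproduces: 28/(1 − 0.20) = 35. The 28 itself does not follow from f = 0.30 with two groups, which needs 45 per group. That is a separate matter. Here 28 and 35 serve only as the group sizes the plan expects to analyse and to enrol.

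**4. Precision**

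Half-widths are in units of the outcome SD, and r is the correlation between preoperative and postoperative values.

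- Unadjusted: t(0.975, 2n−2) × √(2/n). With n = 28: 2.0049 × √(2/28) = 0.536. With n = 35: 0.477.
- ANCOVA, allowing for the lost degree of freedom and the expected baseline imbalance: t(0.975, 2n−3) × √[(2/n)(1 − r²)(1 + 1/(2n−4))]. With n = 28 and r = 0.5: 2.0057 × √(0.07143 × 0.75 × 1.01923) = 0.469.

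The documents do not give r; the range below is an assumption.

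| r | n = 28 | Change from 0.536 | n = 35 (unadjusted 0.477) |
|---|---|---|---|
| 0.1 | 0.538 | +0.5% | 0.478 |
| 0.2 | 0.530 | −1.0% | 0.471 |
| 0.3 | 0.516 | −3.7% | 0.459 |
| 0.4 | 0.496 | −7.4% | 0.441 |
| 0.5 | 0.469 | −12.5% | 0.416 |
| 0.6 | 0.433 | −19.2% | 0.385 |

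Break-even is r = 0.140 at 28 per group and r = 0.124 at 35.

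**5. Downside at r = 0, 28 per group**

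The expected half-width is 0.541, which is 1.0% wider. In a given trial the factor is (t53/t54) × √(1 + T²/54), where t53 and t54 are the 97.5% points and T is the baseline t statistic. At the two-sided 10% point, T = 1.674, it is 1.026. At the 5% point, T = 2.005, it is 1.037. So 1 trial in 10 is at least 2.6% wider and 1 in 20 at least 3.7% wider.

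**6. Missing baselines**

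If two patients per group lack a baseline and are dropped, ANCOVA runs on 26 per group. At r = 0.3 the half-width is 0.537, a ratio of 1.003 to the unadjusted 0.536, so the gain is gone. At r = 0.2 it is 0.552, or 3.0% wider.

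**7. Rank-based fallback**

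Simulation with 20,000 runs, 28 per group and continuous data without ties gave type I error of 4.9% to 5.3%. At an assumed difference of 0.6 SD, power was 57%, 61%, 69% and 74% for r = 0.1, 0.3, 0.5 and 0.6, against about 57% for Mann-Whitney.

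**8. Number of comparisons**

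VAS aside, and with SST included, the schedule gives 3 scores × 4 visits + 1 motion at 2 weeks + 4 motion measures × 3 visits = 25. If external rotation is taken in only one position before surgery, the other position has no matching baseline. That affects 3 of the 25 if the missing position is scapular, or 4 if it is neutral, which is also the 2-week measure.

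**The case against.** The strongest reply is that unadjusted tests are unbiased in a randomised trial, Aim 2 is secondary, and the gain rests on a correlation nobody has stated. All of that is true. A reader might infer that the planned postoperative tests are wrong or biased; nothing in the documents supports that.

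A reader might also take the 1.0% as the most that adjustment could cost. It is an average over chance imbalance, as step 5 shows. Nor is the benefit secure if patients without a baseline are dropped. This matters because preoperative collection rests on the Aim 2a text alone.

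It is tempting to say that the plan definitely tests a preoperative VAS. The wording can equally mean each measure at the times it is collected, so it is ambiguous rather than plainly wrong. It is also tempting to say that the change adds no data and replaces every test one for one. The documents do not establish this, because Aim 2a does not name the motion positions.

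The 23% is an upper bound: scores and motions of one shoulder are unlikely to be independent, and no decision in the plan depends on these tests. Finally, the rank-based fallback was checked only without ties, and it gives a test rather than an interval on the outcome scale.

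These replies limit the claim. They do not explain the missing SST test, the unscheduled V-12 or the wrong product name.

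**Conclusion.** The point holds as a recommended improvement and a list correction, not as a fault that invalidates the analysis. The mismatches for SST, V-12 and the intervention name are certain from the text. The precision gain is conditional: negligible or slightly negative below r of about 0.14, and about 4% to 19% narrower intervals for r from 0.3 to 0.6 at 28 per group. These figures assume a linear relation, equal variances and a baseline value for every patient. The possible loss is small but not capped at 1%.

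**What to change.** Make these changes before unblinding:

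- For each Aim 2 outcome with a preoperative value of the same measure, make the primary analysis an ANCOVA of the postoperative value at each visit on group and that preoperative value. Judge normality on the model residuals. If it fails, use a rank-based ANCOVA (ranks of the outcome on group and ranks of the baseline).
- Keep patients with a missing baseline in the model by single mean imputation of the covariate, computed without regard to group.
- Use the unadjusted test where no matching baseline exists; elsewhere keep it as supporting only.
- Drop the preoperative significance tests and summarise baseline descriptively.
- Add SST to the test list. Remove V-12 or list it as collected. Limit VAS to postoperative times unless preoperative collection is confirmed. Correct the intervention name.
- Add a preoperative row to the visit table that matches Aim 2a and names the range-of-motion positions.

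The cost is SAP wording and one table row. Data collection grows only if the sponsor keeps V-12, adds a preoperative VAS, or adds a second external-rotation position before surgery. Each comparison keeps a single primary test, so their number does not rise beyond the listing of SST.

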Patients will be randomly assigned to one of two treatment groups (see Intervention Description). Patients will randomly select one of 70 sealed envelopes the day of surgery. Patients will be blinded to the medication utilized as well as the treating surgeon (PI). A consecutive series of patients will be enrolled to prevent selection bias. A single surgeon will be performing all procedures to minimize variability. Upon completion of the surgery, a spinal needle will be loaded into the substance of the rotator cuff tendon under direct arthroscopic visualization. The surgeon will then leave the room and the envelope will be opened by the circulating operating room nurse. If the patient is in the treatment group, 2cc of an extracellular matrix graft be opened and then injected with a 22g spinal needle already placed into the bed of the repair by the physician assistant. Those patients that are in the control group will have the needle removed and no injection administered. The envelope will be then sealed with the patient's name and treatment group to allow for data analysis upon completion of the study.

Data Collection will occur post-operatively for 6 months. Data will be collected at 20 timepoints, in total for pain and opioid consumption. For the first seven days, data will be collected at 12-hour time intervals beginning the first evening of the surgery (POD0) at 8pm then at 12-hour intervals for the next 7 days (POD7). Data will be collected using PatientIQ, an application that uses text message or email to collect information. The day of surgery (POD0) the first text will occur at 8pm. Patients will then be notified by text alert 2 times per day (8am and 8pm) asking to rate their pain on a scale of 0-10 (VAS) beginning on POD 1 thru POD 7. Patients will also respond to the number of pain pills taken in the slotted time span. All patients will be prescribed the same narcotic regimen (oxycodone IR) barring any allergies encountered. Patients who fail to respond to the text alert will be notified by the data collection system and contacted via phone by study personnel. Patients lacking smartphone technology will all be notified via telephone and also asked to keep a personal log to capture the information needed.

Data Management

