This research is collecting data on human tissue implants which are routinely used in surgical repair. They are all FDA registered. The following risks can be related to the procedure, study analysis, and medications given:

1. Risk of extracellular matrix injection: Like any medical procedure, there are risks associated with the procedure itself. Theoretical risks associated with the extracellular matrix injection include infection, allergic reaction and injection site irritability. These risks are inherently low risks associated with administration.
2. Risk of text alerts: A HIPPA compliant and password protected database called Patient IQ is the application that will help gather and collect the data. Texting is not a secure form of communication and there is a risk of loss of privacy by entering the data. Measures to lessen these risks include using a password protected database and all personal information will be deidentified with your name removed. In addition, the only information you will provide will be regarding pain level and number of pain pills taken. Your phone number will be kept confidential and not shared with any outside party.

Potential Benefits

An individual benefit from this study is that patients will be monitored closely via text messages two times per day; thus, if any side effects or complications occur related to the injection, the PI will be alerted. Additionally, knowledge gained from this study will allow investigators to determine the most effective treatment methods for minimizing post-operative pain and narcotic use in patients who undergo outpatient rotator cuff surgery. These findings will benefit future patients.

Adverse Event Reporting:

Adverse Events

Recording of Adverse Events

At each contact with the subject, the investigator will seek information on adverse events by specific questioning and, as appropriate, by examination. Information on all adverse events should be recorded immediately. All clearly related signs, symptoms, and abnormal diagnostic procedures results should be recorded in the source document.

Notification of Adverse Events

All adverse events will be reported according to WIRB guidelines.

Ethical Considerations

N/A

Funding Source

N/A

Subject Stipends or Payments

N/A

Publication Plan

The paper will be submitted for publication in the Journal of Shoulder and Elbow Surgery or the Journal of Bone and Joint Surgery upon completion.

References

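### The protocol credits the twice-daily texts with alerting the PI to injection side effects, but the texts ask only about pain and pills, and patients who reply by text have no scheduled adverse-event question before the POD 14 visit

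*Combined protocol and SAP*

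**What the plan says.** Four parts of the combined protocol and SAP bear on this.

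- **Potential Benefits** names the texts as the safety mechanism: "patients will be monitored closely via text messages two times per day", from which it concludes that "if any side effects or complications occur related to the injection, the PI will be alerted".
- **Potential Risks**, in the item on text alerts, limits what the texts carry: "the only information you will provide will be regarding pain level and number of pain pills taken".
- **Research Design** and **Study Visits/ Study Duration** describe the same content. The alerts go out at 8am and 8pm, "asking to rate their pain on a scale of 0-10 (VAS) beginning on POD 1 thru POD 7", and "Patients will also respond to the number of pain pills taken in the slotted time span". The schedule section adds: "Data concerning pain and narcotic use will be collected via text message (or phone if patients fail to respond to text messages". Twice-daily collection covers only the first week: "For the first week, twice per day (12-hour increments), patients will self-report VAS pain".
- **Recording of Adverse Events** sets a general rule: "At each contact with the subject, the investigator will seek information on adverse events by specific questioning".

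Research Design and Study Outcome Measures also provide telephone contact for patients who do not answer a text and for patients without a smartphone. Data Management gives the PI access to the database.

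**The concern.** Potential Benefits presents close monitoring as something an individual patient gains by taking part, and the texts are the stated means. A message that asks for a pain score and a pill count cannot directly report an infection, an allergic response or local irritation, which are the theoretical injection risks the protocol itself lists. If the general adverse-event rule does not reach these patients either, early problems come to light only when a patient volunteers them or recalls them two weeks later. At stake are the accuracy of a benefit claim in the protocol and the prompt detection of problems after an added biologic injection.

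**Working it through.** The plan gives no figure to reproduce here. The check is a count of scheduled contacts and a comparison of sections.

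**Step 1. Count the early prompts** (table in Study Visits/ Study Duration).
- POD 0: one prompt, at 8PM.
- POD 1 to 7: two a day, 7 × 2 = 14.
- Total: 1 + 14 = 15.
- Prompts listing anything other than VAS and number of pain pills: 0 of 15.

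**Step 2. Find the gap.**
- The last first-week prompt is POD 7 at 8PM. The next scheduled contact is on POD 14 (office exam, then an 8PM prompt).
- Days with nothing scheduled: POD 8 to POD 13, 13 − 8 + 1 = 6 days.
- If the POD 14 exam were at 8AM (an assumption; the table gives no hour), the gap would be 7 × 24 − 12 = 156 hours.
- The later prompts, on POD 14, 21, 28 and 42, also list only VAS and pills.

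**Step 3. Look for an alert route.** Research Design, Data Management, Study Outcome Measures, Study Visits and the adverse-event section describe no symptom question, free-text field, threshold that triggers an alert, or rule for when the PI reviews replies. The one automatic notification described concerns failure to reply.

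**Step 4. Test the each-contact rule against the texts.** There are two readings.
- *A text is a contact.* The rule then requires an adverse-event question in it, which contradicts the sentence in Potential Risks that limits texts to pain and pills.
- *A text is not a contact.* A patient who answers every text then has no scheduled adverse-event questioning until the POD 14 office exam.

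Under either reading the sections do not fit together.

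**Step 5. Test the telephone route.** Calls are live contacts before POD 14, so the rule could apply to them. But study personnel make the calls to non-responders, whereas the rule assigns the questioning to the investigator, and the stated purpose of those calls is to obtain the missing pain or pill data. If callers did ask about adverse events, early questioning would depend on missing a text or lacking a smartphone, not on a planned contact that every patient has.

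**The case against.** The strongest reply is that the plan already has an ascertainment rule: the investigator asks about adverse events at every contact, and telephone contact does occur in the first week. A reader might infer from the texts' content that no early safety monitoring exists, or that every early contact is an automated message. The documents support neither inference. The rule is written down, and patients without smartphones and non-responders are telephoned. What remains is that neither the rule nor the calls give a patient who answers every text a scheduled adverse-event question before POD 14.

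Second, pain scores and pill counts are not empty of safety information. An infection or local irritation could show as rising pain, and the PI can see the database. This stands as an indirect signal. But no review rule is given, pain after cuff repair is not specific to an injection problem, and an allergic reaction need not show this way at all.

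Third, the sentence limiting text content is a privacy assurance, not a safety specification. That is a fair reading of its purpose, but the schedule independently lists the same content.

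Fourth, a reader might infer that a planned comparison of safety between arms is left incomplete. No such comparison appears in the aims, the endpoints or the Statistical Analysis Plan. The scheduled contacts are the same in both arms and patients are blinded, so nothing here shows that ascertainment would differ by arm. Nor can it be said what patients are told in the consent form, which is not in the material reviewed; the point concerns the protocol's own benefit statement.

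**Conclusion.** The point holds in this form: the protocol attributes to the texts a safety function for which it describes no mechanism, and it does not tie its general adverse-event rule to any scheduled contact before POD 14 for patients who reply by text. In size, 0 of 15 prompts from POD 0 to POD 7 carry an adverse-event item, and six further days have no scheduled contact.

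This assumes that the texts contain what the schedule and Potential Risks say and nothing more, and that no unpublished call script or app setting adds a safety question. If either exists, the protocol should say so, and the point reduces to a wording correction. The matter is worth fixing because it concerns patient safety and the remedy is cheap. It does not touch the pain, opioid or functional endpoints or their analysis.

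**What to change.** Add one yes/no question to the existing text, for example: any new problem or side effect since your last message? Put the same question in the telephone script, so that text and phone patients are asked alike, and have the system flag a yes to the PI. Asking about any new problem suits the blinding, since neither the patient nor the PI knows whether an injection was given. Amend the sentence in Potential Risks that limits texts to pain and pill counts; otherwise the new item creates a fresh contradiction with the privacy assurance. State in Recording of Adverse Events that this item is how the each-contact rule is met for patients who reply by text.

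If no item is added, delete the benefit statement and say which contacts the each-contact rule covers, so that the benefit statement, the text content and the rule agree.

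The cost is one question in an application already in use, matching wording edits, slightly more burden for patients and some call-backs. Treatment, randomisation and sample size are unchanged.
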